5.0 ANALYSIS POPULATIONS

The Analysis Populations to be used for the analyses in this study are described below.

5.1 Intent-to-Treat (ITT) Population

Includes all subjects who were randomized based on the as randomized principle (i.e. according to the treatment they were randomized to).

5.2 Per-Protocol (PP) Population

Includes all subjects in ITT who complete the Week 12 visit without any deviations considered to have substantial impact on the primary effectiveness outcome.

5.3 Safety Population

Includes all subjects who were treated with *Restylane® Defyne* or randomized to no treatment control group. Subjects are analyzed based on the as treated principle (i.e. according to the treatment actually received).

The primary and secondary effectiveness analyses will be performed using the ITT analysis set. The primary and the first secondary effectiveness analysis will be repeated using the PP analysis set if there is at least a 10% difference in the number of subjects between the PP and ITT sets. The safety evaluations will be performed based on the safety analysis set.

6.0 SUBJECT DISPOSITION

Subject disposition will be summarized in a table. The number of subjects screened and randomized will be presented. The number of subjects in the Safety, ITT and PP populations will be summarized. The number and percentage of subjects in the ITT population who complete the study will be summarized, along with the number and percentage of subjects who do not complete the study for each discontinuation reason as specified on the eCRFs.

Data will be summarized by treatment group and overall except for the number of subjects screened.

All withdrawn subjects will be listed individually, including at least subject number, date and reason for withdrawal, and last visit performed.

Inclusion/exclusion data will be presented by subjects in a data listing.

7.0 PROTOCOL DEVIATIONS

Protocol deviations will be presented by subject in a data listing. Subjects with protocol deviations will be listed individually, including subject number and observed deviation. Depending on the seriousness of the deviation, subject

👶 GALDERMA

might be excluded from the PP population, which shall be documented prior to database lock.

8.0 DEMOGRAPHIC AND BASELINE CHARACTERISTICS

8.1 Demographic and Baseline Characteristics

Demographic endpoints, baseline assessments, and subject characteristics will be presented based on the ITT population using descriptive statistics by treatment, as appropriate. Some of the variables to be summarized are described below (other variables maybe added dependent on final eCRF):

Table 1: Fitzpatrick Skin Types (FST)

Skin type	Skin color	Skin characteristics
Ι	White; very fair; red or blond hair; blue eyes; freckles	Always burns, never tans
II	White; fair; red or blond hair; blue, hazel or green eves	Usually burns, tans with difficulty
III	Cream white; fair with any eye or hair color; very common	Sometimes mild burn, gradually tans
IV	Brown; typical Mediterranean Caucasian skin	Rarely burns, tans with ease
V	Dark brown; Middle Eastern skin types	Very rarely burns, tans very easily
VI	Black	Never burns, tans very easily

Continuous variables will be summarized with descriptive statistics (number of subjects, mean, SD, median, minimum, and maximum). Categorical variables will be summarized using counts and percentages.

Demographic and baseline characteristics will be presented by treatment and subject in data listings.

8.2 Medical History

History of relevant surgical events and medical conditions, including any prior dermatological procedures or implants, are collected.

Medical history will be summarized by individual treatment group and overall for the ITT population as given below:

9.0 EFFICACY VARIABLES

9.1 Primary Efficacy Variable

Response rates, where a responder is define

9.2 Secondary Efficacy Variables

The secondary efficacy variables are:

10.0 EFFICACY ANALYSIS

All efficacy variables will be summarized at each scheduled visit for the ITT population. Categorical variables will

Page **13** of **37**

10.2 Secondary Efficacy Analysis

Title

11.0 STATISTICAL/ANALYTICAL ISSUES

11.1 Handling of Dropouts or Missing Data

Number of missing values will be summarized and reported as appropriate. For ITT analysis

11.2 **Pooling of Centers in Multi-Center Studies**

There will be no pooling of centers.

11.3 **Multiple Comparisons/Multiplicity**

No adjustments for multiple comparisons or multiplicity will be made.

11.4 **Examination of Subgroups**

11.5 **Interim Analysis and Data Monitoring**

There is no interim analysis planned for this study.

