#### 2.3 Study rationale

The rationale of performing this study is to obtain evidence of safety and effectiveness of Restylane® Defyne in the chin for augmentation and correction of chin retrusion to support a future US marketing application.

Chin projection is an important component of facial appearance and affects the overall balance and harmony of the face. In clinical practice, surgical techniques, such as osteotomy or insertion of implants are commonly used for correction of chin retrusion.

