3.0 OVERALL STUDY DESIGN AND OBJECTIVE

3.1 Study Objectives

3.1.1 Primary Effectiveness Objective

The primary objective of the study is to evaluate the effectiveness of *Restylane® Defyne* versus a no-treatment control in the correction of chin retrusion by comparing response rates, defined by at least 1 point improvement from baseline using

, as assessed by the Blinded Evaluator, at 12 weeks after last injection for the treatment group or after baseline if randomized to no treatment.

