4.0 GENERAL ANALYSIS CONVENTION

Data collected in this study will be documented using summary tables and subject data listings. Continuous endpoints will be summarized using descriptive statistics, e.g. number of subjects, mean, median, standard deviation, minimum and maximum values. Categorical endpoints will be presented in frequency tables with number and percentage of observations for each level.

Confidence intervals will be two-sided and constructed at a confidence level of 95%. Statistical tests will be performed at a significance level of 5%, and p-values will be two sided.

Study days will be calculated relative to the date of first dose of study product for subjects randomized to Treatment and relative to the date of randomization for subjects randomized to No Treatment. Day 1 will be the first day of study product administration in the study for the subjects randomized to Treatment and the day of randomization for the subjects randomized to No Treatment. The day prior to Day 1 will be Day -1. There will be no Day 0.

Baseline will be the last assessment prior to the first dose of study product for subjects randomized to Treatment and the last assessment prior to the randomization for subjects randomized to No Treatment. For analysis purpose, the date of randomization will be considered as the date of first dose for subjects who are randomized to No Treatment.

Adverse events and Medical History will be coded using Medical Dictionary for Regulatory Activities (MedDRA), Version 21.0. Concomitant medications will be coded using the World Health Organization (WHO) Drug Dictionary (Mar 2018).

Data for all subjects in the clinical database will be included in the data listings. Calculated (derived) variables will be listed as appropriate. All tables, listings, and figures will be programmed using SAS Version 9.3 or higher. A list of proposed statistical tables, listings, and figures is provided in Section 16.0. Any changes from the SAP will be detailed in the CSR.

Effective date: 2018-09-20 12:05

43USCH1702 Statistical Analysis Plan

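### SAP 11.3 rules out any multiplicity adjustment: if two or more secondary endpoints are tested between arms at 5%, their joint false-positive rate exceeds 5%

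*SAP*

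**What the plan says.** The readable text on this point is short.

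- **Level of each test.** SAP 4.0: "Statistical tests will be performed at a significance level of 5%, and p-values will be two sided". The sentence is general and makes no distinction between primary and secondary endpoints.
- **Multiplicity.** SAP 11.3, in full: "No adjustments for multiple comparisons or multiplicity will be made".
- **More than one secondary.** SAP 9.2 opens in the plural, "The secondary efficacy variables are", and the list itself is redacted. The paragraph on analysis sets at the end of SAP 5.3 says "The primary and the first secondary effectiveness analysis will be repeated using the PP analysis set" (if the two sets differ enough in size). A first secondary analysis implies at least a second.
- **Analysis set.** The same paragraph says "The primary and secondary effectiveness analyses will be performed using the ITT analysis set".
- **One visible primary comparison.** SAP 3.1.1 describes one comparison of response rates, treatment against no treatment, at 12 weeks. SAP 11.5 plans no interim analysis.
- **Purpose.** Protocol 2.3 says the study is to provide evidence of safety and effectiveness "to support a future US marketing application".

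The content of SAP 3.1.2, 9.2 and 10.2, and most of Protocol section 10 before 10.5, is redacted.

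**The concern.** A general 5% level combined with a blanket rule against adjustment leaves the status of a significant secondary result open. If two or more secondaries are compared between arms, each carries its own 5% risk of a false positive and nothing in the readable text bounds the risk for the set. In a trial intended to support a marketing application, someone reading the report could take a secondary p-value below 0.05 as established when no error rate was controlled for it.

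What is at stake is the strength of any secondary claim. The primary conclusion is not at risk: there is one visible primary test and no interim look, so it keeps its stated level.

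**Working it through.** **Inputs**

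- Level per test: α = 0.05, two-sided (SAP 4.0).
- Adjustment: none (SAP 11.3).
- Number of secondaries tested between arms, m: not readable. The plural in SAP 9.2 and the reference to a first secondary analysis support at least two secondaries, but do not show that both are tested. m = 2 and m = 3 are therefore assumptions.
- Correlation ρ between test statistics: not given. Values from 0 to 0.9 are assumed.
- All m null hypotheses true, which is the worst case.

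**Step 1: the plan's own figure.** For one test, 1 − (1 − 0.05) = 0.05. This matches the stated 5%. The readable text gives no familywise error rate to reproduce.

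**Step 2: independent tests.** The chance of at least one false positive is 1 − (1 − α)^m.

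- m = 2: 1 − 0.95² = 1 − 0.9025 = 0.0975, or 9.8%.
- m = 3: 1 − 0.95³ = 1 − 0.8574 = 0.1426, or 14.3%.

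Whatever the correlation, the rate cannot exceed m × α: 10% for two tests and 15% for three.

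**Step 3: correlated tests.** Endpoints that rate the same treated chin are likely to be positively correlated. Simulating equally correlated two-sided z-tests (400,000 draws) gives:

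| ρ | m = 2 | m = 3 |
|---|---|---|
| 0 (exact, Step 2) | 9.75% | 14.3% |
| 0.3 | 9.4% | 13.6% |
| 0.5 | 9.05% | 12.6% |
| 0.8 | 7.8% | 9.9% |
| 0.9 | 7.0% | 8.3% |

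Every entry is above 5%. The rate returns to 5% only if the tests are perfectly correlated, or if just one secondary is tested.

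**Step 4: effect of a fixed order.** Suppose the primary is tested first and the confirmatory secondaries follow in a set order, each at 5%, stopping at the first non-significant result. A false positive then requires rejection of the first true null in the sequence, which happens with probability at most 5%. The bound covers the primary and the confirmatory secondaries together, for any correlation and any mix of true and false nulls. No test is run below 5%, so the primary loses no power.

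**The case against.** The strongest case on the other side has four parts.

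**The relevant sections are redacted.** A gatekeeping rule or a statement that secondary p-values are nominal could sit in SAP 10.2 or in Protocol section 10. A fixed sequence tests every endpoint at the full 5%, so it could even stand beside a sentence that rules out adjustments. The SAP is also based on protocol version 3.0, while the protocol supplied is version 5.0, so a later rule cannot be excluded. This stands: one cannot say that the plan lacks a hierarchy. What can be said is that 11.3 is a complete, unqualified sentence that points to none.

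**No secondary hypothesis test is visible.** SAP 4.0 sets the level for tests that are done; it does not say that each secondary is tested. SAP 10.0 speaks of summaries: "All efficacy variables will be summarized at each scheduled visit for the ITT population". Some secondaries may be descriptive or confined to one arm. This also stands, and it makes the point conditional on two or more between-arm tests.

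**The inflation may be modest.** A reader might infer a large excess, since five or ten independent tests would give 22.6% or 40.1%. Nothing readable supports those counts. With two tests the rate is at most 10%, and 7 to 8% if they are highly correlated. A reader might also take the phrase about the first secondary analysis as evidence of a ranking that the plan then ignores. It is used only to say which analysis is repeated in the per-protocol set, and may be no more than list numbering.

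**Secondaries may be supportive only.** That is a legitimate position, and then no adjustment is needed. But the readable text does not say so, and no readable text proposes a secondary claim either. The status is simply not stated where it can be seen, and it should be settled before results are known.

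**Conclusion.** The point holds in conditional form. SAP 11.3 excludes multiplicity adjustment, SAP 4.0 sets tests at two-sided 5%, and there is more than one secondary efficacy variable. If two or more secondaries are tested between arms, the chance of at least one false positive exceeds 5%: about 9.8% for two independent tests, 14.3% for three, and 7 to 8% for two tests correlated at 0.8 to 0.9.

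These figures assume that every tested secondary null is true. The number of tests and their correlation are also assumptions, because the list and the methods are redacted. The documents do not support saying that the error is many times 5%, that a testing order exists and is ignored, or that no hierarchy exists anywhere in the plan. The visible primary comparison is unaffected. This is an inexpensive improvement worth making in a trial meant to support a marketing application, and not a threat to the main result.

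**What to change.** Replace SAP 11.3 with text along these lines:

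> The primary endpoint is tested first at two-sided 5%. Only if it is significant are the secondary endpoints designated as confirmatory tested, in an order fixed before database lock, each at two-sided 5%, stopping at the first p ≥ 0.05. All other secondary, exploratory and subgroup p-values are nominal. Secondary endpoints without a between-arm test are descriptive.

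The sponsor should name the confirmatory secondaries and their order. The list in SAP 9.2 cannot be read here, so its sequence should not be adopted by default. If none is meant to be confirmatory, saying so is enough. If the redacted sections or the later protocol version already contain a hierarchy, 11.3 should be reconciled with it.

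The cost is one paragraph, with no extra subjects and no loss of power for the primary. The downside is that an endpoint late in the order may lose a formal claim if an earlier one fails.

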12.0 EXTENT OF EXPOSURE

Data of extent of exposure and treatment procedure will be summarized for initial treatment, optional touch-up (only for subjects randomized to treatment), optional initial treatment (only for subjects randomized to no treatment), and optional re-treatment (only for subjects randomized to treatment) separately for safety population. Following parameters will be summarized for extent of exposure:

Extent of exposure data will be presented by subject in data listings.

Following parameters will be summarized for treatment procedure:

Procedural Anesthetics and Injection Concomitant Procedures data will be presented by subject in data listings.

13.0 SAFETY ANALYSIS

The safety endpoints include:

- Evaluation all adverse events (AEs).
- Pre-defined, injection related events (IREs) reported during the first 4 weeks after treatment as recorded in the subject diary.
- Presence of any unexpected lumpiness or non-uniform density by palpation of the chin at each physical follow-up visit.
- Presence of any mass formation in the chin at baseline and at each physical visits thereafter.
- Presence of abnormal lower lip movement, function, and sensation (on three different locations) according to pre-defined methods, at baseline and at each physical follow-up visit.
- Presence of abnormal chin function and sensation (on three different locations) according to pre-defined methods, at baseline and at each physical follow-up visit.

13.1 Adverse Events

Adverse events (AEs) will be summarized for the safety population. All AEs will be coded using MedDRA and presented by MedDRA system organ class (SOC), preferred term (PT), and treatment.

Only AEs occurring after first injection for subjects randomized to Treatment or after randomization for subjects randomized to No Treatment will be included in analysis. AEs occurring before, if any, will only be listed in subject data listings.

All AE endpoints will be summarized by treatment as follows:

- i) No treatment at baseline, includes subjects randomized to No Treatment up until the time of their first injection.
- ii) Initial treatment with Restylane Defyne, includes subjects randomized to Defyne (after their first treatment up until their

🖧 GALDERMA	43USCH1702 Statistical Analysis Plan

Title

iii)

optional retreatment) pooled with the controls (i.e., subjects randomized to No Treatment) after their optional initial treatment. Retreatment with Restylane Defyne, includes subjects randomized

to Defyne after their optional retreatment.

A summary of AEs will be provided, which will include:

- i) number of subjects with at least one AE and number of events (in total as well as serious AEs)
- ii) number of subjects with at least one AE, related to study product or injection procedure, and number of events (in total as well as serious AEs)
- iii) number of subjects with at least one AE, unrelated to both study product and injection procedure, and number of events (in total as well as serious AEs)
- iv) number of subjects who did not have an AE

AEs will be summarized by SOC, PT, and severity.

The number of subjects with AEs related to study product or injection procedure as well as the number of events will be summarized by SOC, PT, and severity. Untreated subjects in control group cannot have a related AE and hence cannot be included in this table.

In addition, for related AEs, the number of days to onset and the duration of event will be summarized by SOC and PT using mean, SD, min, max and median.

Time to onset of an AE will be derived as the start date minus the date of most recent treatment. If the start date is missing, it will be assumed that the AE started on the day of most recent treatment.

Duration of an AE will be derived as the stop date minus the start date + 1. If the start date is missing, it will be assumed that the AE started on the day of most recent treatment. Missing stop date will not be imputed and therefore no duration will be calculated in these cases. Instead, the number of AEs that were ongoing at the end of the study will be given.

If a subject has more than 1 AE of the same PT and there are different grades of severity, only the highest grade will be represented in the summary of severity. If the severity assessment is missing, the highest level of severity will be assumed.

•• G	ALDERMA	43USCH1702 Statistical Analysis Plan	Doc id
		Each AE will be assessed for relatedness to the study product injection procedure. The Investigators will be asked to indicat to each of the following questions in the eCRF: "Do you consider that there is a reasonable possibility	t and for the e a response

Action taken for related AEs will also be summarized.

To evaluate consistency of the results across different subgroups, AEs will also be analyzed across different subgroups as described in the exploratory objectives (see Section 3.1.4).

All reported AEs will be listed in data listings including time to onset, duration of AE and timing of the AE. Timing would be the variable indicating whether the AE occurred after no treatment, initial treatment, or optional retreatment.

By-subject listings also will be provided for all subjects (safety population) for the following: AEs related to study product or injection procedure, AEs resulting in discontinuation of study product, and serious AEs.

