### 4.3 Duration of subject participation

A subject may be involved in the study for approximately 17.5 months from screening to the final follow-up visit. "End of study" is defined as the time point when the last subject has completed the last study visit.

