#### 8.9.4 Reporting of adverse events

Adverse event reporting on each subject should start after the subject has been randomized. The reporting should continue during each follow-up visit (including telephone contacts and extra visits between planned visits) until the last scheduled visit in the study.

All AEs, non-serious as well as serious, are to be reported as an AE in the eCRF.

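### Initial-treatment and re-treatment AE columns have different follow-up windows and populations, and the visible SAP gives no subject-time or common window, so crude values for later-onset and background AEs are not directly comparable

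*SAP*

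**What the plan says.** SAP 13.1 summarises all AE endpoints in three columns: (i) controls before any injection, (ii) initial treatment and (iii) re-treatment.

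- Column (ii) is "Initial treatment with Restylane Defyne, includes subjects randomized to Defyne (after their first treatment up until their" (the sentence runs over a page break) "optional retreatment) pooled with the controls (i.e., subjects randomized to No Treatment) after their optional initial treatment".
- Column (iii) is "Retreatment with Restylane Defyne, includes subjects randomized" "to Defyne after their optional retreatment".
- SAP 12.0 confirms that re-treatment is a choice and is confined to one arm: "optional re-treatment (only for subjects randomized to treatment".
- Onset is counted from the latest injection: "Time to onset of an AE will be derived as the start date minus the date of most recent treatment". SAP 13.1 summarises it for related AEs only, by mean, SD, minimum, maximum and median.
- Protocol 8.9.4 continues AE reporting "until the last scheduled visit in the study", and Protocol 4.3 puts an outer limit on the time available: "A subject may be involved in the study for approximately 17.5 months from screening to the final follow-up visit".

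The overall AE summaries in SAP 13.1 count subjects and events. Percentages come from the general convention for categorical endpoints in SAP 4.0. No AE denominator is stated for any column.

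**The concern.** Protocol 2.3 says the trial is meant to support a US marketing application. A table with neighbouring columns for initial treatment and re-treatment invites the reader to ask whether a repeat injection is as safe as the first. If one column has followed its subjects for longer, it collects more background and late-onset AEs whatever the risk per month. Its recorded onset times can also run longer, because the other column is cut off sooner by the end of the study. A short re-treatment window could then reassure falsely, and a long one could alarm falsely. Column (iii) is also self-selected, so its subjects need not resemble those in column (ii).

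**Working it through.** The plan gives no figure to reproduce. The check is of windows and populations first, then an illustration under stated assumptions.

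**1. Who contributes what time (SAP 12.0 and 13.1, Protocol 8.9.4)**

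| Subjects | Column | Time starts | Time ends |
|---|---|---|---|
| Defyne arm, re-treated | (ii) | first treatment | re-treatment |
| The same subjects | (iii) | re-treatment | last visit |
| Defyne arm, never re-treated | (ii) | first treatment | no visible cut-off before last visit |
| Controls who take treatment | (ii) | their optional treatment | no end stated |

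For a re-treated subject who completes the study, a longer stay in (ii) leaves less time in (iii). Column (ii) is a mixture of three groups, so it is more than the time before re-treatment.

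**2. Mechanism in one re-treated Defyne subject.** Assumptions: 17.5 months in all (Protocol 4.3; this overstates treated time because it counts from screening), r months left after re-treatment, and the same constant hazard λ in both phases, set so that the 12-month risk is 10% or 30%. Then λ = −ln(0.9)/12 = 0.00878 or −ln(0.7)/12 = 0.0297 per month, and P(at least one AE in t months) = 1 − exp(−λt).

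| r (months) | 10% hazard: before v after | 30% hazard: before v after |
|---|---|---|
| 3 | 12.0% v 2.6% | 35.0% v 8.5% |
| 6 | 9.6% v 5.1% | 29.0% v 16.3% |
| 12 | 4.7% v 10.0% | 15.1% v 30.0% |

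Mean onset among events within a window t is 1/λ − t·exp(−λt)/(1 − exp(−λt)). At the 10% hazard this gives 7.10 v 1.49 months for r = 3 and 2.73 v 5.89 months for r = 12. If a touch-up counts as the most recent treatment, onset in (ii) restarts there and the contrast changes again.

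**3. Why these are not column values.** Add never-re-treated Defyne subjects, followed for the full 17.5 months: 1 − exp(−0.00878 × 17.5) = 14.2%. With an assumed 50% uptake and the 10% hazard, the Defyne part of (ii) becomes:

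- r = 3: (12.0 + 14.2)/2 = 13.1%, against 2.6% in (iii)
- r = 6: (9.6 + 14.2)/2 = 11.9%, against 5.1%
- r = 12: (4.7 + 14.2)/2 = 9.5%, against 10.0%

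The clear reversal at r = 12 nearly vanishes. Treated controls would move the result again. With r, uptake and the control windows not legible, no figure here describes the planned table.

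**4. Events soon after injection.** Assume 20% of subjects ever have such an event, with exponential onset of mean 3 or 7 days. P = 20% × (1 − exp(−t/mean)). For r = 1, 3 and 6 months this gives 19.7 to 20.0% after re-treatment and 20.0% before it. The window hardly matters for these events.

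**5. Denominator.** Suppose the true risk among re-treated subjects is 10% and uptake is 30 to 90%. Divided by re-treated subjects, column (iii) reads 10%. Divided by all Defyne-randomised subjects, it reads 0.30 × 10 = 3% to 0.90 × 10 = 9%.

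**6. Does subject-time remove the effect?** Under the assumptions of step 2 the expected rate is 100λ, that is 0.88 or 2.97 events per 100 subject-months, in either window and for any r. It removes the window effect but not the selection.

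**The case against.** The strongest reply is that nothing in the visible plan compares (ii) with (iii). The columns are descriptive, with no test, margin or statement that re-treatment is as safe as first treatment. That stands, and it limits the point to interpretation.

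The redactions also matter. The visit schedule, the exposure parameters under SAP 12.0 and the table list in SAP 16 are not legible, so an exposure adjustment or a denominator may sit there. The 17.5 months comes from protocol version 5.0, whereas the SAP is based on version 3.0.

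A reader might infer more than the documents support:

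- *That percentages and onset times must differ, or that re-treatment must look safer.* Only the windows and populations differ by design. The direction depends on timing that cannot be read.
- *That these columns are the only evidence on repeat injection.* SAP 13.2 plans a 28-day diary counted from the day of treatment and not limited to the first injection, although the visible text does not spell out a diary after re-treatment. SAP 13.0 adds palpation, mass, function and sensation checks at physical visits. The diary does not reach later events.
- *That subjects who tolerated the first treatment badly will decline a second.* The documents say nothing about who opts in. Self-selection is a fact of the design, but its direction is unknown.
- *That late reactions to re-treatment are lost.* Protocol 8.9.7 asks for related AEs with onset after the study ends to be reported if the investigator learns of them. This is not systematic collection, and such events may not enter the onset table, but the route exists.

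**Conclusion.** The concern holds in a limited form. The crude subject counts, percentages and onset summaries in columns (ii) and (iii) come from unequal, unadjusted windows and from different populations, so for later-onset and background AEs they are not comparable even at equal risk. Events close to injection are little affected. The size and direction of any distortion are not established: the figures in the working show the mechanism under an assumed constant hazard, with assumed timing and uptake. The conclusion rests on the column definitions in SAP 13.1, on re-treatment being optional and confined to one arm, and on no subject-time, common window or denominator appearing in the legible text. No planned test is biased. This is a worthwhile, low-cost improvement to the safety reporting.

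**What to change.** In SAP 13.1:

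1. For columns (i) to (iii), add subject-months at risk and events per 100 subject-months. State that the denominator for each column is the subjects who entered that phase, and state when each subject's time in column (ii) ends, including controls and never-re-treated Defyne subjects.
2. Add one descriptive table restricted to re-treated subjects, showing all AEs and related AEs in an equal, pre-specified window after initial treatment and after re-treatment. The window should be no longer than the shorter of the two planned follow-up periods. Say whether a touch-up restarts it.
3. Add a note that raw percentages and onset times in (ii) and (iii) are not to be compared directly.

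The cost is SAP wording and one or two extra descriptive tables, built from treatment and AE dates that the onset calculation already needs. No trial procedure or effectiveness analysis changes. There are three drawbacks. The equal-window table leaves out later events, which stay in the full tables. Rates per subject-month assume roughly constant risk over time, which suits background AEs better than acute reactions. The re-treated-only table still describes subjects who chose a second treatment, so it should be labelled descriptive.
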